## Abbreviations

ADE	Adverse Device Effect
AE	Adverse Event
AQUA	Institut für angewandte Qualitätsförderung und Forschung
BfArM	Bundesinstitut für Arzneimittel und Medizinprodukte
CC	CharitéCenters
CE	Conformité Européenne
CEA	Cost effectiveness analysis
CIP	Clinical investigation plan
CP	Conditional power
CRC	Clinical Research Center for Hair and Skin Science
CRF	Case report form
DD	Device deficiency
DTI	Deep tissue injury
ED	Emergency department
EPUAP	European Pressure Ulcer Advisory Panel
ICER	Incremental cost effectiveness ratio
ICF	Informed consent form
ICU	Intensive care unit
IIS	Investigator initiated study
LOCF	Last observation carried forward
NPUAP	National Pressure Ulcer Advisory Panel
PPPIA	Pan Pacific Pressure Injury Alliance
PU	Pressure ulcer
PUCLAS	Pressure ulcer classification
QM	Clinical Quality and Risk Management
RR	Relative risk
SADE	Serious Adverse Device Effect
SAE	Serious adverse event
SD	Source data
SOP	Standard operating procedure
TMF	Trial master file

## 1 Administrative Information

### 1.1 Title

A randomized controlled parallel-group trial to investigate the effectiveness of two silicone dressings for sacral and heel pressure ulcer prevention compared to no dressings

### 1.2 Trial registration

The study is registered at <https://clinicaltrials.gov/>. The ClinicalTrials.gov Identifier is NCT02295735.

### 1.3 Protocol version

Version 4 of September 29, 2015

### 1.4 Funding

This investigator initiated study (IIS) is conducted by the Clinical Research Center for Hair and Skin Science, Department of Dermatology and Allergy, Charité – Universitätsmedizin Berlin. on behalf of the Central Quality Management (QM) of the Charité-Universitätsmedizin Berlin. The trial is supported by Mölnlycke Healthcare AB. Mölnlycke provides the silicone dressings Mepilex® Border Sacrum and Mepilex® Border Heel for the intervention group.

## 2 Introduction

### 2.1 Background and Rationale

Pressure ulcers (PUs) are severe forms of skin and tissue lesions caused by prolonged compression and deformation of soft tissues. PU prevalence and incidence is high especially in high risk settings like geriatric, long-term or intensive acute care. According to the latest Global Burden of Disease Study 2010 PUs were assigned the highest disability index (Hay et al. 2014). In adults the majority of PU occurs at the heels and at the sacral area (Kottner, Raeder 2014). The occurrence of PUs in hospitals is widely accepted as an unwanted adverse outcome in patient care. PU incidence and/or hospital acquired PU prevalence are widely accepted indicators of the quality of care (Kottner, Lahmann 2013; Unbeck et al. 2013). In Germany PU incidence figures are regularly used to make country wide comparisons of PU prevention and treatment performance in hospitals (AQUA 2012). However, effective and efficient PU prevention especially in high risk settings is still challenging and there is a high need to optimize prevention further.

PU prevention includes the identification of PU risk and the application of preventive measures. Mobility and activity limitations are the most important PU risk factors. The cornerstone of PU prevention is repositioning, early mobilization and the use of special support surfaces (National Pressure Ulcer Advisory Panel (NPUAP), European Pressure Ulcer Advisory Panel (EPUAP), Pan Pacific Pressure Injury Alliance (PPPIA) 2014). In addition, there is emerging evidence that the application of dressings on pressure ulcer predilection sites may help to prevent PU development (Clark et al. 2014). In the latest Pressure Ulcer Prevention and Treatment Guideline the use of prophylactic dressings is considered as an emerging preventive intervention (NPUAP, EPUAP, PPPIA 2014). Preventive dressings on intact skin might reduce friction and shear forces and/or modify the microclimate (Park 2014, Santamaria et al. 2013a). Both mechanisms might protect the skin and underlying tissues from pressure/deformation injury. Because this new approach might potentially further reduce PU incidence, thus increasing hospital patient safety, the Clinical Quality and Risk Management of the Charité-Universitätsmedizin Berlin decided to investigate, whether these dressings are also effective at the Charité-Universitätsmedizin Berlin.

## 2.2 Objectives

### Primary objective

- To determine if preventive silicone dressings (Mepilex® border) applied to the heels and to the sacrum in addition to PU standard prevention reduce the cumulative PU incidence category II, III, IV, and deep tissue injury (DTI) compared to PU standard prevention alone in at high or very high risk hospital patients.

### Secondary objectives

- To determine if preventive silicone dressings (Mepilex® border) applied to the heels and to the sacrum in addition to PU standard prevention reduce the PU incidence density category II, III, IV, and deep tissue injury (DTI) compared to PU standard prevention alone in at high or very high risk hospital patients.
- To determine if preventive silicone dressings (Mepilex® border) applied to the heels and to the sacrum in addition to PU standard prevention reduce the cumulative PU incidence category I compared to PU standard prevention alone in at high or very high risk hospital patients.
- To determine if preventive silicone dressings (Mepilex® border) applied to the heels and to the sacrum in addition to PU standard prevention reduce the PU incidence density category I compared to PU standard prevention alone in at high or very high risk hospital patients.
- To determine if preventive silicone dressings (Mepilex® border) applied to the heels and to the sacrum in addition to PU standard prevention increase days free of PUs category I, and category II, III, IV, and DTI compared to PU standard alone in at risk hospital patients.
- To determine if preventive silicone dressings (Mepilex® border) applied to the heels and to the sacrum in addition to PU standard prevention are cost effective.

## 2.3 Trial design

A randomized, controlled, two arm, superiority pragmatic trial will be performed with a 1:1 allocation to the intervention and control groups. After completion of 50% of the subjects an interim analysis will be conducted to allow potential early stopping (futility stopping based on conditional power) (see 6.2).

### 3 Methods: Participants, interventions, and outcomes

#### 3.1 Study setting

The study will be conducted at the Charité university hospital (Berlin, Germany) in critically ill and/or trauma patients who are admitted to the emergency department and/or to intensive care units (ICUs).

#### 3.2 Eligibility criteria

##### Inclusion criteria

- Age 18+ years
- Major trauma and/or critically ill surgical and/or internal patients (e.g. with cardiac arrest) admitted to the emergency department and being transferred and/or admitted or directly to a surgical or internal ICU
- Major trauma and/or critically ill surgical and/or internal patients admitted through an in-house hospital transfer to a surgical or internal ICU (e.g. postoperative complications or acute deterioration of general health)
- Being at “high” or “very high” PU risk according to the Charité PU prevention standard:
  - Category 3 (=care dependent/limited bed mobility)
  - 4A (= high care depended, limited mobility in bed)
  - 4B (= high care dependent, totally immobile) according to the Jones classification modified by Charité
- Expected minimum length of stay at least three days
- Informed consent (or by legal representative)

##### Exclusion criteria

[figure not shown]
- Patients at end of life/dying patients
- Existing PU or other skin/tissue lesion (e.g. scars) at heels or sacral skin
- Positioning on air fluidized beds
- Known allergy to Mepilex® dressings
- Patients who cannot be repositioned due to medical reasons (e.g. cardiovascular instability, suspected or actual spinal cord injury)
- Trauma to sacrum and/or heels
- Exclusion based on complicated or not possible positioning of patients with the following diagnoses (ICD-10-GM version 2015): 66.2; J80.0; S06.-; G93.2; I60.-; I63.-
- Exclusion due to certain procedures (OPS version 2015): 8-390.0; 8-390.3; 8-390.4; 8-852

As this study does not involve any drugs, systemic agents or any other invasive techniques, patients would be eligible even if they participate in another trial.

### 3.3 Interventions

Within the study PU prevention for all patients follows the Charité university hospital pressure ulcer prevention standard (Charité-Universitätsmedizin Berlin 2012) (Figure 1).

Figure 1. Current pressure ulcer prevention standard at the Charité

This includes PU risk scoring and skin inspection within 6 hours after admission and depending on the risk categories “high risk” and “very high risk” the implementation of preventive measures including: (1) patient information, (2) daily skin inspection, (3) mobilization, (4) use of special support surfaces, (5) repositioning and (6) floating heels. Regarding general skin and incontinence care there are no other standards implemented at the moment.

In case of potentially meeting the inclusion criteria for the study a researcher/research assistant of the CRC team will check the in- and exclusion criteria using a screening form. If eligible the assignment to one of the study groups will be performed by this researcher. This will be also done within 6 hours after admission **to the ICU**.

If a patient is assigned to the intervention group the dressings Mepilex® Border Sacrum and Mepilex® Border Heel will be applied by the researcher/research assistant onto the respective intact skin areas according to the instructions of the manufacturer and according to the study SOP (see Appendices 1 and 2). Special care will be taken that the Mepilex® Border Sacrum is carefully applied and that no other skin care products are used between the skin and the dressings. The dressings will be renewed every 3 days by the researcher/research assistant. In case of becoming soiled or dislodged they are changed immediately by the nurses and/or by the researchers. Nurses on the participating ICUs and on general wards will be instructed accordingly. In addition, in the intervention group laminated patient cards will be posted at and/or near the bed serving as reminder and containing minimum information about how to apply the dressings and the contact of the responsible researcher (Appendix 3). Dressings remain onto the skin during the whole study period also including transfer to another ward. All other PU preventive care and treatment procedures are performed as usual according to the Charité PU prevention standard (Figure 1).

Skin and tissue inspections are conducted and study variables are collected daily by instructed researchers/research assistants/study nurses in agreement with the ICU and general ward staff. The following educational activities will be conducted before and during the trial:

- Initiation visit/kick-off meeting explaining the study design, procedures, data collection and documentation methods
- One hour skin and PU classification instruction, followed by an online examination PUCLAS3 (Beeckman, Schoonhoven 2014) for all study nurses/research assistants doing skin examinations
- Unannounced patient visits by the principle investigator for duplicate data collection and skin examination

Research assistants/study nurses/researchers follow up all included patients once daily for ensuring study compliance, monitoring correct dressing use and fit, doing skin inspections at the heels and sacral area and for monitoring the health condition including daily

documentation of PU risk and resource use regarding dressings and possible PU treatment (dressings, wound care procedures).

The study/follow-up ends if:

- The patient is no longer at “high” or “very high” PU risk according to the Charité standard (Figure 1) and if no sacral or heel PU developed or
- Complete healing of a within the study period developed heel or sacral PU or
- An adverse event (AE) related to the preventive dressings occurred or
- The patient wishes to withdraw or
- A severe form of protocol violation occurred (e.g. non-wearing of the dressings for more than 24 hours) or
- The patient dies or
- The patient is transferred to another care setting outside the Charité Campus Virchow or is discharged from the hospital

Adherence to the study protocol is improved using the following strategies:

- Kick-off meetings and training on the participating ICUs and EDs
- Subject cards at the bedside (Appendix 3)
- Once daily follow-up visits and assessments by researchers including checks of dressing fit
- Monthly status reports about recruitment on the participating wards
- Unannounced patient visits by the PI for duplicate data collection and skin examination

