### 3.4 Outcomes

#### Primary outcome

Name	Method and metric	Time points of data collection
Pressure ulcer category II, III, IV, Unstageable, DTI at heels or sacrum	
 
• Clinical assessment using the NPUAP/EPUAP 2014 PU classification system
 
• Proportions developed from baseline until end of study (cumulative incidence)
 
	D0 and once daily

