**Figure 3. Data collection and management**

## 5.2 Statistical methods

Depending on the level of measurement (nominal, ordinal, continuous) variables will be described using absolute and relative frequencies or arithmetic means, medians and spread parameters (minimum, maximum, interquartile ranges, standard deviations). Baseline demographic (age, gender, PU risk etc.) and clinical characteristics (e.g. medical diagnoses, duration of ventilation) of each group will be displayed in a table.

The primary end point PU incidence category II, III, IV, DTI at heels and/or sacrum will be compared using a Chi-squared test. This will be the main analysis of this primary outcome. A logistic regression will be applied to adjust for baseline covariates. An alpha level of 5% (two-sided) will be applied. Kaplan-Meier analyses and logrank test will be used to compare the times to development of a new PU between groups. Multiple Cox regression analysis will be performed to adjust for potential confounders. Data will be analysed as intention to treat.

Secondary outcomes will be analysed in a similar way. Depending on the level of measurement (nominal, ordinal, continuous) secondary outcomes will be described using absolute and relative frequencies or arithmetic means, medians and spread parameters (minimum, maximum, interquartile ranges, SDs). Chi-squared or t-tests will be applied to compare groups. In case of normality assumption being violated, the Mann-Whitney U test will be used instead of t-test.

For daily measurements, missing values will be imputed via LOCF method, and the results will be compared to those without imputation.

A cost effectiveness analysis (CEA) comparing both groups will be conducted. Quantities of used preventive dressings including labor costs for application in the intervention group and quantities of used PU treatment materials (e.g. dressings, time) will be documented. Current market prizes in Euro will be used to calculate the total costs per group. An incremental cost effectiveness ratio (ICER) will be calculated by dividing the mean differences in costs by the mean differences in effects. In order to make results comparable a similar approach like the work by Santamaria et al. 2013b will be used.

All analytic steps including the CEA will be repeated for the two subgroups heel PUs and sacral PUs.

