
d) Ziehen Sie nacheinander die seitlichen Schutzfolien langsam ab und streichen Sie den Schaumverband nach außen hin aus. Überprüfen Sie, ob der Verband richtig positioniert ist sowie faltenfrei und fest an der Haut haftet.
	
d) Run side of hand along gluteal cleft to ensure secure placement. Gently smooth each side into place.

	

e) Variante A – Produktapplikation/ Figure A - Product placement.

[figure not shown]

[figure not shown]

e) Variante B – Produktapplikation/ Figure B - Product placement inverted.

f) Lagern Sie den Patienten in seitlicher Position oder auf den Rücken.
	
f) Remove the patient in a site or back position

4. Besondere Hinweise
 
a) Tägliche Überprüfung des Verbandes und Dokumentationsführung.
 
b) Achten Sie darauf, dass die Verbandränder bei Entfernung oder Erneuerung des Schaumverbandes faltenfrei, glatt und fest kleben.
 
c) Der Verbandwechsel erfolgt alle 3 Tage und so lang der Patient einem Risiko ausgesetzt ist.
	
4. Special Instructions
 
a) Daily assessment of the dressing and documentation.
 
b) Removal and reapplication of dressing. Ensure the border of the dressing is smooth/even with no wrinkles.
 
c) Remove and replace dressing after 3 days as long as the patient is still at risk.

5. Mögliche Störungen / Problemlösungen
 
a) Die Auflagefläche muss trocken und frei von Pflegeprodukten und eventuellen Pflasterresten sein, damit der Schaumverband gut auf der Haut haftet.
 
b) Keine zusätzlichen Pflegeprodukte verwenden.
	
5. Possible Error / Problem Solutions
 
a) The application area must be dry and free of dimethicone, skin sealants, emollients and remove the center release film for good adhesion.
 
b) Don't use any other additional products.

6. Lagerung und Reinigung
 
a) Gestalten Sie Ihren Arbeitsplatz übersichtlich und sauber.
 
b) Lagern Sie die Wundverbände (Mepiplex® Border Sacrum) trocken und bei Raumtemperatur.
	
6. Storage Conditions/Cleaning
 
 
• Clean and tidy up your workplace
 
• Store the dressings Mepiplex® Border Sacrum at room temperature in a dry place.
 

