### Category/Stage I: Nonblanchable Erythema

Intact skin with non-blanchable redness of a localized area usually over a bony prominence. Darkly pigmented skin may not have visible blanching; its color may differ from the surrounding area.

The area may be painful, firm, soft, warmer or cooler as compared to adjacent tissue. Category/Stage I may be difficult to detect in individuals with dark skin tones. May indicate "at risk" individuals (a heralding sign of risk).

[figure not shown]

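### The end-of-follow-up rules make the length of primary-outcome observation depend on category I pressure ulcers, and on the literal wording a patient still at high risk can leave when a category I clears

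*Combined protocol and SAP*

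**What the plan says.** Section 3.3 of the protocol lists events that end the study for a patient, joined by 'or'. Two matter here.

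- Rule 1: the patient is no longer at high or very high risk "and if no sacral or heel PU developed". This is the only rule tied to risk status.
- Rule 2: "Complete healing of a within the study period developed heel or sacral PU". It names no category and sets no risk condition.

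Section 3.4 defines the primary outcome as "Pressure ulcer category II, III, IV, Unstageable, DTI at heels or sacrum", with the metric "Proportions developed from baseline until end of study (cumulative incidence", so the count stops at each patient's own end of study. Category I is a secondary outcome in the same section and is described there as a pressure ulcer, as it is in Appendix 4. Section 3.4 also contains the only definition of healing, which is full epithelialisation. Appendix 4 defines category I as a lesion of intact skin.

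Section 5.2 makes the chi-squared test on proportions the main analysis, by intention to treat. Kaplan-Meier, log-rank and Cox analyses are also planned. It adds: "All analytic steps including the CEA will be repeated for the two subgroups heel PUs and sacral PUs".

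**The concern.** Rule 2 can end observation for the primary event because of something that is not a primary event. Take a very-high-risk patient with sacral category I on day 3 that clears on day 5. Read literally, the study ends there. A deep tissue injury on day 9 goes unrecorded, and the patient counts as free of the primary outcome. No section provides for observation after that exit.

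Rule 1 works the other way. A patient with an unhealed category I stays under daily inspection after risk has fallen, whereas an ulcer-free patient leaves at that point.

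The length of observation therefore turns on category I. Section 2.2 asks, as a secondary objective, whether the dressings reduce category I, so observation time could differ between arms because of treatment. A comparison of simple proportions does not adjust for that. In the time-to-event analyses, censoring at healing may be informative, because Appendix 4 says category I may mark at-risk individuals ("a heralding sign of risk"). Intention to treat cannot restore observations that were never made.

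Healing at one site also ends observation of the other, which affects the separate heel and sacral analyses.

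**Working it through.** **Step 1. Who is affected under each reading of 'healing'**

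| Patient | Healing includes clearance of category I | Healing means closure of an open ulcer only |
|---|---|---|
| No ulcer, risk falls | Leaves (Rule 1) | Leaves (Rule 1) |
| Category I clears, still at high risk | Leaves (Rule 2); a later primary event is not recorded | Stays |
| Category I not cleared, risk falls | Stays | Stays |
| Category I cleared earlier, risk falls later | Has already left | Stays: an ulcer developed, so Rule 1 fails; nothing epithelialised, so Rule 2 fails |
| Category II or worse heals | Leaves; primary event already counted, but the other site is no longer observed | Same |

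Under the second reading, the patient in the fourth row can leave only by the remaining exits, such as discharge, transfer or death. Both columns make the primary window depend on category I.

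**Step 2. The plan's own sample size**

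Inputs from Section 3.6: 0.06 against 0.01, two-sided alpha 0.05, power 0.80, chi-squared test, 211 per arm. With pooled variance under the null and mean proportion 0.035:

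n = [1.96 × √(2 × 0.035 × 0.965) + 0.8416 × √(0.06 × 0.94 + 0.01 × 0.99)]² / 0.05² = [0.5094 + 0.2167]² / 0.0025 = 210.9

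This rounds up to 211, as stated. Expected primary events are 211 × 0.06 = 12.7 in controls and 211 × 0.01 = 2.1 with dressings.

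**Step 3. Sensitivity to lost events**

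The documents give no rate of category I, of its clearance, or of later category II or worse ulcers. Let f be the assumed share of primary events lost through Rule 2. Observed rates become 0.06(1 − f) and 0.01(1 − f) if both arms lose events, or 0.06(1 − f) and 0.01 if only controls do. Exact power sums the two binomial distributions (211 per arm) over all outcomes where the pooled chi-squared test rejects at 0.05.

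| f | Control events lost | Observed control rate | Exact power, both arms | Exact power, controls only |
|---|---|---|---|---|
| 0 | 0 | 6.0% | 0.849 | 0.849 |
| 5% | 0.6 | 5.7% | 0.83 | 0.81 |
| 10% | 1.3 | 5.4% | 0.80 | 0.77 |
| 20% | 2.5 | 4.8% | 0.75 | 0.68 |
| 30% | 3.8 | 4.2% | 0.68 | 0.56 |

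The normal approximation behind the 211 starts at 0.80 and falls to 0.78, 0.76, 0.70 and 0.64 (both arms), or 0.77, 0.73, 0.64 and 0.54 (controls only). The decline is similar; only the starting point differs.

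The opposite effect, extra observation under Rule 1, cannot be quantified because no rate for it is given.

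**The case against.** The best counter-argument is the healing definition. Intact skin has nothing to re-epithelialise, so complete healing can be read as closure of an open ulcer. By then the primary event is already counted and Rule 2 loses none. The bare term 'PU' does not settle the matter: Section 3.6 uses it without a category when sizing a trial whose endpoint is category II or worse. This stands, so loss of events through Rule 2 is the literal reading and not an established fact. It does not remove the problem, because Rule 1 still ties the window to category I.

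The route to a lost event is also narrow. A category I that progresses never heals and is counted. A loss needs full clearance, continuing high risk, continued stay on the campus, and then a new category II or worse ulcer. At f = 5% in both arms exact power is 0.83, and at 10% it is still 0.80, the planned level. The lowest figures come from assuming that no dressing patient is affected. All of this stands.

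A reader might infer that patients whose category I has cleared are those most likely to have the primary event. Appendix 4 says only that category I may indicate risk; it says nothing about patients in whom it has resolved.

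**Conclusion.** The point holds in this form: whichever way healing is read, how long a patient is observed for the primary outcome depends on category I, a post-randomisation event that the dressing may change, and the main test ignores this. On the literal wording, primary events in patients still at risk can also go unrecorded, and no analysis can recover them.

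The size is unknown. The power figures rest on assumed loss shares and on the planning rates of 6% and 1%. They show only that, with about 15 expected events in all (12.7 + 2.1 = 14.8), small losses matter.

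A reader might infer a bias toward no effect, with more control patients leaving early. The documents do not support a net direction. Early exits would remove control events, longer retention under Rule 1 would add control observation, and both presuppose an effect on category I that the trial is meant to test.

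**What to change.** Amend Sections 3.3 and 3.4 so that the primary-outcome window does not depend on the occurrence or healing of category I.

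- For every patient in both arms, continue daily skin inspection and recording of category II, III, IV, Unstageable and DTI until loss of high or very high risk status, death, transfer, discharge or withdrawal. Inspections after loss of risk status count only for the healing outcome.
- For the heel and sacral analyses in Section 5.2, apply the window to each site separately, so that neither an event nor healing at one site ends observation of the other.
- Reconcile Sections 3.3 and 3.4 on whether healing covers category I.
- Reconcile the passages on dressing wear. Section 3.3 ties it to the study period, while the SOP in Appendix 1 says "Remove and replace dressing after 3 days as long as the patient is still at risk" and Appendix 2 has a similar instruction. The change above concerns observation only, and this review does not propose what should apply to the dressings in these patients.

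The exits for dressing-related adverse events and severe protocol violations are a separate question, not covered here.

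The cost is an amended rule, a sentence defining the window, and some extra daily inspections in patients whose ulcer clears while they are still at risk. Section 3.3 already provides for daily inspection.

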## Secondary outcomes

Name	Method and metric	Time points of data collection
Pressure ulcer category II, III, IV, Unstageable, DTI at heels or sacrum	
 
• Clinical assessment using the NPUAP PU classification system
 
• Proportions developed per 1000 bed days (incidence)
 
	D0 and once daily
Pressure ulcer category I (non-blanchable erythema) at heels and/or sacral area	
 
• Clinical assessment using the NPUAP PU classification system
 
• Proportions developed from baseline until end of study (cumulative incidence)
 
	D0 and once daily
Pressure ulcer category I (non-blanchable erythema) at heels and/or sacral area	
 
• Clinical assessment using the NPUAP PU classification system
 
• Proportions developed per 1000 bed days (incidence)
 
	D0 and once daily
Days free of sacral and/or heels pressure ulcers category I, II, III, IV, DTI	
 
• Clinical assessment using the NPUAP PU classification system
 
• Number
 
	D0 and once daily
Resources associated with heel and sacral PU prevention	
 
• Preventive dressings (n), time for dressing application (minutes; data source: estimation)
 
• Type of support surface (standard, special elastic foam, viscoelastic foam, low air loss overlay/mattress, alternating air mattress; data source: clinical records and direct observation)
 
• Type of turning (30° degrees left/right, supine, prone, other; data source: clinical records)
 
	D0 and once daily
Resources associated with heel and sacral PU treatment	
 
• Wound assessments (number and times; data source: clinical records and estimation)
 
• Wound infection diagnoses, e.g. swabs, biopsies (number, times; data source: clinical records and estimation)
 
• Therapeutic primary and secondary dressings (numbers, types), time for dressing application/changes (minutes; data source: clinical records and estimation)
 
• Debridement (numbers and types incl. material; data source: clinical records and estimation)
 
• Systemic antimicrobial treatment because of PU wound (number, types; data source: clinical records)
 
	D0 and once daily

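### Outcome follow-up stops at dressing non-wear or a dressing-related adverse event, which only the dressing arm can have, so later ulcers go unrecorded in that arm despite the stated intention to treat

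*Combined protocol and SAP*

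**What the plan says.** Section 3.3 lists the events that end a patient's study participation and follow-up. Two concern the dressing: "An adverse event (AE) related to the preventive dressings occurred", and "A severe form of protocol violation occurred (e.g. non-wearing of the dressings for more than 24 hours"). The others are shared by both arms: no longer at high or very high risk and without an ulcer, healing of an ulcer that developed in the study, withdrawal, death, and transfer or discharge. The dressings are applied in the intervention group only, and the title (1.1) gives the comparator as no dressings.

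Section 3.4 defines the primary metric as "Proportions developed from baseline until end of study (cumulative incidence"), so the 3.3 list sets each patient's outcome window. A secondary outcome uses "Proportions developed per 1000 bed days (incidence"). Section 5.2 makes a chi-squared test the main analysis, adds "Kaplan-Meier analyses and logrank test will be used to compare the times to development of a new PU between groups" with Cox regression, and states: "Data will be analysed as intention to treat". Its only missing-data rule is last observation carried forward (LOCF) for daily measurements, compared with results without imputation.

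On exposure to the stop rule, 3.3 says of the dressings: "In case of becoming soiled or dislodged they are changed immediately by the nurses and/or by the researchers". Study staff "follow up all included patients once daily".

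**The concern.** A control patient cannot fail to wear a dressing or react to one. Controls are therefore observed to the shared end events, while some dressing-arm patients stop being observed earlier for reasons tied to the treatment. Ulcers they develop afterwards are not recorded. Patients can still be analysed in their allocated arm, but the outcome data that an intention-to-treat comparison needs would not exist.

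The other planned analyses do not repair this. The chi-squared test ignores observation time. Logrank and Cox would censor these patients as if exit were unrelated to ulcer risk, in one arm only. Incidence per bed day corrects for time but not for informative exit. LOCF, if applied after exit, would carry an ulcer-free status forward. The interim conditional power (6.2) and the cost-effectiveness ratio (5.2) would use the same truncated data.

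**Working it through.** **1. The plan's own figure.** Inputs from 3.6: 6% v 1%, two-sided alpha 0.05, power 0.80. The pooled two-proportion formula without continuity correction gives n = 210.9, so 211 per arm, with power 0.800 at 211. The total is 422 × 1.10 = 464.2, stated as 464 (232 per arm). The plan's figure reproduces.

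**2. Model for lost ulcers.** Let q be the share of the dressing arm leaving by the two dressing-specific events, and f the share of their ulcer risk still to come at exit. The documents give neither, so both are assumed. Exits are counted as no ulcer, the direct reading of 3.4 with all randomised patients analysed. Exiters are given average risk. With no true effect:

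- recorded dressing-arm incidence = 0.06 × (1 − q × f)
- expected unrecorded ulcers = 211 × 0.06 × q × f

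**3. False result favouring the dressing.** Both binomials were enumerated exactly at 211 per arm. A result counts when the uncorrected chi-squared test has p < 0.05 and the dressing arm is lower.

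| q | f | Recorded incidence | Unrecorded ulcers | False result favouring dressing |
|---|---|---|---|---|
| 0 | – | 6.00% | 0 | 2.4% |
| 2% | 50% | 5.94% | 0.1 | 2.5% |
| 5% | 30% | 5.91% | 0.2 | 2.6% |
| 5% | 50% | 5.85% | 0.3 | 2.8% |
| 10% | 30% | 5.82% | 0.4 | 2.8% |
| 10% | 50% | 5.70% | 0.6 | 3.2% |
| 20% | 30% | 5.64% | 0.8 | 3.4% |
| 20% | 50% | 5.40% | 1.3 | 4.3% |
| 30% | 80% | 4.56% | 3.0 | 9.3% |

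The 30% rows for f reflect 7.3, which says risk is highest in the first days. At 232 per arm the results barely change: 2.8%, 3.3% and 4.5% for q = 5%, 10% and 20% with f = 50%, against 2.4% with no exits.

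**4. Plausible range of q.** The loss allowance adds 464 − 422 = 42 patients. If all 42 were such exits, that would be 42/232 = 18% of the dressing arm. The last row is therefore extreme. Section 7.1 says dressing adverse events have not been reported, which points to the low end.

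**5. If the dressing works only while worn.** Suppose 3.6's 1% applies during wear and exiters revert to 6% for the remaining share f. The true dressing-arm incidence is 0.01 + 0.05 × q × f; the recorded one is 0.01 × (1 − q × f). At q = 10%, f = 50%, these are 1.25% and 0.95%, so the relative risk is recorded as 0.16 (0.95/6) when it is 0.21 (1.25/6).

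**The case against.** Five points deserve weight.

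*Direction.* The bias favours the dressing only if exits stay in the denominator as ulcer-free. If ulcer-free exiters were dropped instead (232 randomised per arm, half the risk remaining), the recorded dressing-arm incidence would rise to 6.3% at 10% exits and 6.7% at 20%. A false result favouring the dressing would then occur in 1.8% and 1.2% of trials, and one against it in 3.4% and 4.9%. This arithmetic is right, so the direction is conditional. But dropping randomised patients from one arm also contradicts intention to treat, and LOCF would, if anything, support the ulcer-free count.

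*Time-to-event analyses.* The model gives exiters average risk, and in that case Kaplan-Meier and logrank do allow for shorter follow-up. This stands. However, they are not the main analysis, and whether non-wear or skin reaction is unrelated to ulcer risk cannot be checked once observation stops.

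*Routine records.* The hospital standard includes daily skin inspection, and 5.1 uses routine documentation as source data, so some later ulcers might be found in ward notes. Partly right. Yet 5.1 lists ulcer categories among the data collected specifically for the study, and no section plans retrieval after exit.

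*Size.* Immediate replacement, daily fit checks and bedside cards keep exits rare. At 2–5% exits with half the risk remaining, 0.1–0.3 ulcers are lost. Total two-sided error stays at 4.8%, 4.9% and 5.5% for 5%, 10% and 20% exits with half the risk remaining. This stands and limits the importance of the point.

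*Other violations.* Non-wear is only an example of a severe violation, so other violations could end follow-up in controls too. True, but the two named events remain one-sided.

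**Conclusion.** The concern holds. The 3.3 stop rules and the intention-to-treat statement in 5.2 cannot both be met as written, because outcome observation ends on treatment-specific events in one arm. This follows from the text and needs no assumed number.

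The size does rest on assumptions: the exit share, the risk remaining, average risk in exiters, and exits counted as ulcer-free. Over 2–20% exits with 30–50% of the risk remaining, the inflation is modest, at most 4.3% against 2.4% in the direction of the dressing. With only about 2 dressing-arm ulcers expected (1% of 211), the effect estimate is more exposed than the significance test. The point should be fixed, though it does not by itself overturn the design.

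**What to change.** - **3.3:** Separate the end of dressing use from the end of outcome observation. Remove protocol violation (including non-wear) and dressing-related adverse event from the events that end outcome follow-up. Continue the daily heel and sacrum inspections in both arms to the shared end events. Record non-wear and dressing-related events with date and reason, and report their counts.
- **5.2:** Analyse all randomised patients by allocated arm. State how patients with early end of follow-up are counted in the chi-squared test, and whether LOCF applies after exit. Keep the analysis truncated at exit as a labelled sensitivity analysis.
- **3.6:** State whether the expected 1% is an intention-to-treat figure.

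This concerns outcome data only, not when a dressing is stopped or resumed.

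The cost is wording plus some inspection days by staff who already visit daily. If the 1% is an on-treatment figure and exiters revert to control risk, the intention-to-treat effect is smaller. With half the risk remaining:

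| Exits | Dressing-arm incidence | Power at 211 per arm | n per arm for 80% | Power at 232 per arm, none lost |
|---|---|---|---|---|
| 5% | 1.125% | 77% | 226 | 81% |
| 10% | 1.25% | 74% | 242 | 78% |
| 20% | 1.5% | 68% | 279 | 72% |

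The change must be made before enrolment finishes: study-grade inspections that were never made cannot be added at analysis.
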